Appendix 5 Classification of Adverse Events of Special Interest

AE of Special Interest	PT Code	PT Term
Hepatic dysfunction-related	10001547	Alanine aminotransferase abnormal
Hepatic dysfunction-related	10001551	Alanine aminotransferase increased
Hepatic dysfunction-related	10003477	Aspartate aminotransferase abnormal
Hepatic dysfunction-related	10003481	Aspartate aminotransferase increased
Hepatic dysfunction-related	10058477	Blood bilirubin abnormal
Hepatic dysfunction-related	10005364	Blood bilirubin increased
Hepatic dysfunction-related	10062685	Hepatic enzyme abnormal
Hepatic dysfunction-related	10060795	Hepatic enzyme increased
Hepatic dysfunction-related	10068237	Hypertransaminasaemia
Hepatic dysfunction-related	10024690	Liver function test abnormal
Hepatic dysfunction-related	10077692	Liver function test increased
Hepatic dysfunction-related	10062688	Transaminases abnormal
Hepatic dysfunction-related	10054889	Transaminases increased
Hepatic dysfunction-related	10019670	Hepatic function abnormal
Myopathy-related	10028372	Muscular weakness
Myopathy-related	10028320	Muscle necrosis
Myopathy-related	10028334	Muscle spasms
Myopathy-related	10028411	Myalgia
Myopathy-related	10028653	Myositis
Myopathy-related	10028625	Myoglobin blood increased
Myopathy-related	10059888	Myoglobin blood present
Myopathy-related	10028631	Myoglobin urine present
Myopathy-related	10058735	Myoglobinaemia
Myopathy-related	10028629	Myoglobinuria
Myopathy-related	10028641	Myopathy
Myopathy-related	10028648	Myopathy toxic
Myopathy-related	10074769	Necrotising myositis
Myopathy-related	10033425	Pain in extremity
Myopathy-related	10039020	Rhabdomyolysis
Myopathy-related	10005468	Blood creatine phosphokinase abnormal
Myopathy-related	10005470	Blood creatine phosphokinase increased
Myopathy-related	10005477	Blood creatine phosphokinase MM increased
Tendon rupture/disorder-related	10043248	Tendon rupture
Tendon rupture/disorder-related	10028331	Muscle rupture
Tendon rupture/disorder-related	10039227	Rotator cuff syndrome
Tendon rupture/disorder-related	10074599	Tendon discomfort
Tendon rupture/disorder-related	10043239	Tendon disorder
Tendon rupture/disorder-related	10043242	Tendon injury
Tendon rupture/disorder-related	10069650	Tendon necrosis
Tendon rupture/disorder-related	10066371	Tendon pain
Tendon rupture/disorder-related	10043255	Tendonitis
Diabetes-related	10005554	Blood glucose abnormal
Diabetes-related	10005557	Blood glucose increased
Diabetes-related	10012601	Diabetes mellitus
Diabetes-related	10012607	Diabetes mellitus inadequate control
Diabetes-related	10012671	Diabetic ketoacidosis
Diabetes-related	10018429	Glucose tolerance impaired
Diabetes-related	10018478	Glucose urine present
Diabetes-related	10018473	Glycosuria

AE of Special Interest	PT Code	PT Term
Diabetes-related	10018484	Glycosylated haemoglobin increased
Diabetes-related	10020635	Hyperglycaemia
Diabetes-related	10056997	Impaired fasting glucose
Diabetes-related	10023379	Ketoacidosis
Diabetes-related	10023388	Ketonuria
Diabetes-related	10023391	Ketosis
Diabetes-related	10067585	Type 2 diabetes mellitus
Diabetes-related	10057597	Urine ketone body present
Renal dysfunction-related	10069339	Acute kidney injury
Renal dysfunction-related	10005481	Blood creatinine abnormal
Renal dysfunction-related	10005483	Blood creatinine increased
Renal dysfunction-related	10005846	Blood urea abnormal
Renal dysfunction-related	10005851	Blood urea increased
Renal dysfunction-related	10050760	Blood urea nitrogen/creatinine ratio increased
Renal dysfunction-related	10068447	Creatinine renal clearance abnormal
Renal dysfunction-related	10011372	Creatinine renal clearance decreased
Renal dysfunction-related	10018356	Glomerular filtration rate abnormal
Renal dysfunction-related	10018358	Glomerular filtration rate decreased
Renal dysfunction-related	10030302	Oliguria
Renal dysfunction-related	10072370	Prerenal failure
Renal dysfunction-related	10038435	Renal failure
Renal dysfunction-related	10061480	Renal function test abnormal
Renal dysfunction-related	10062237	Renal impairment
Metabolic acidosis	10027417	Metabolic acidosis
Hypoglycemia-related	10005554	Blood glucose abnormal
Hypoglycemia-related	10005555	Blood glucose decreased
Hypoglycemia-related	10020993	Hypoglycaemia
Hypoglycemia-related	10021000	Hypoglycaemic coma
Hypoglycemia-related	10021002	Hypoglycaemic encephalopathy
Hypoglycemia-related	10048803	Hypoglycaemic seizure
Hypoglycemia-related	10040576	Shock hypoglycaemic
Cognitive dysfunction-related	10057668	Cognitive disorder
Cognitive dysfunction-related	10010305	Confusional state
Cognitive dysfunction-related	10013395	Disorientation
Cognitive dysfunction-related	10027175	Memory impairment
Cognitive dysfunction-related	10048294	Mental status changes
Cognitive dysfunction-related	10001949	Amnesia
Elevated uric acid-related	10005861	Blood uric acid increased
Elevated uric acid-related	10020903	Hyperuricaemia
Elevated uric acid-related	10018627	Gout
Decreased hemoglobin-related	10018884	Haemoglobin decreased
Decreased hemoglobin-related	10018838	Haematocrit decreased
Decreased hemoglobin-related	10002034	Anaemia

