Clinical Laboratory Test Value Changes: It is the investigator/subinvestigator's responsibility to review the results of laboratory tests for each individual subject as they become available. This review will be documented by the investigator/subinvestigator's dated signature on the laboratory report. The investigator or subinvestigator may repeat the laboratory test or request additional tests to confirm the results of the original laboratory tests. If this laboratory test value is considered medically relevant (ie, clinically significant) by the investigator or subinvestigator (subject is symptomatic, requiring corrective treatment or further evaluation), or if the laboratory test value leads to discontinuation, and/or fulfills a seriousness criterion, this is considered an AE. However, if an abnormal result is found in a test performed at the central laboratory and is considered an AE, the course should be confirmed with the test results of the central laboratory in principle.

Severity: Adverse events will be graded on a 3-point scale below:

- |                      |  |
|----------------------|--|
| 1 = Mild:     | Discomfort noticed, but no disruption to daily activity.         |
| 2 = Moderate: | Discomfort sufficient to reduce or affect normal daily activity. |
| 3 = Severe:   | Inability to work or perform normal daily activity.              |

**IMP Causality:** Assessment of causal relationship of an AE to the use of the IMP is defined as follows:

- Related:** There is a reasonable possibility of a temporal and causal relationship between the IMP and the AE.
- Not Related:** There is no temporal or causal relationship between the IMP and the AE.

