### 8.8.2 Eliciting and Reporting Adverse Events

The investigator or subinvestigator will regularly assess the subjects for the occurrence of AEs. To avoid bias in eliciting AEs, subjects should be asked the nonleading question: “How have you felt since your last visit?” All AEs (serious and nonserious) reported by the subject must be recorded on the source documents and eCRF provided by the sponsor. Adverse event collection will begin after a subject signs the ICF and will continue until the end of the follow-up period. All AEs must be recorded in the eCRF after subject informed consent has been obtained, including screening failures due to AEs, irrespective of trial intervention. In this trial, AEs during the treatment and follow-up periods will be assessed compared to Day 1.

Medical terminology should be used for AE reporting. Adverse events should be reported as a single unifying diagnosis whenever possible or, in the absence of a unifying diagnosis, as individual signs or symptoms.

Exacerbation or disease progression should be reported as an AE only if there are unusual or severe clinical features that were not present, or experienced earlier, or not expected based on the course of the condition. A reported AE that undergoes worsening in severity or seriousness should be reported as a new AE in the eCRF. However, if worsening of the condition is observed on Day 1 or later, the AE should be reported as a new AE in the eCRF without limiting to worsening in severity or seriousness. If a subject is suspected to have COVID-19 during the trial, the investigator or subinvestigator will confirm the results of an antigen test, etc., and take necessary measures such as a determination on the necessity for discontinuation of the IMP in consideration of the safety of the subjects. A positive result will be reported as an AE in the eCRF.

In addition, the sponsor must be notified immediately by e-mail in principle of any IREs according to the procedure outlined below, in [Section 8.8.3](#). Special attention should be paid to recording hospitalization and concomitant medications.

The AE, start date, end date, seriousness, severity, relationship to trial treatment (IMP causality), action taken with trial treatment, and outcome will be recorded on the source documents and in the eCRF.

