##### **9.4.2.1 Adverse Events**

All AEs will be coded by system organ class and Medical Dictionary for Regulatory Activities preferred term. The incidence of the following events will be summarized:

- Treatment-emergent AEs
- TEAEs by severity
- TEAEs causally related to the IMP
- TEAEs with an outcome of death
- Serious TEAEs
- TEAEs leading to discontinuation of the IMP
- TEAEs of special interest (including muscle-related TEAE and TEAE associated with hepatic impairment)

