9.2.1 Adverse Events of Special Interest

The incidence of AEs of special interest will be calculated by SOC and PT.

Adverse events of special interest that are potentially causally related to the IMP will be summarized in the same manner. The classification of the AEs of special interest is shown in [Appendix 5](#).

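### The hepatic AESI list in SAP Appendix 5 contains no liver-injury diagnosis, so an event coded only to such a diagnosis would be absent from the AESI tables

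*SAP*

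**What the plan says.** SAP 9.2.1 states that "The incidence of AEs of special interest will be calculated by SOC and PT" and then that "The classification of the AEs of special interest is shown in" Appendix 5. It has no clause for related terms and names no standard MedDRA query. The protocol offers no other term list: 8.8.1 says that no AESIs have been identified for the product, and 8.8.5 is marked not applicable. Appendix 5 is thus the only operative definition.

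The hepatic group there ends with "Hepatic function abnormal"; the terms before it are laboratory findings. Other groups are wider: the muscle group includes "Rhabdomyolysis" and the renal group includes "Acute kidney injury".

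On the reporting side, Protocol 8.8.2 says: "Adverse events should be reported as a single unifying diagnosis whenever possible". Individual signs or symptoms are to be used only when there is no such diagnosis. Protocol 9.4.2.1 includes this item among the planned adverse event summaries: "TEAEs of special interest (including muscle-related TEAE and TEAE associated with hepatic impairment").

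**The concern.** The reporting rule and the counting rule pull in different directions. A site that follows Protocol 8.8.2 and diagnoses hepatitis would record hepatitis rather than a raised ALT. The SAP would then not recognise that event as a hepatic AESI, because the term is not in Appendix 5.

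Safety is the primary objective, and hepatic events are one of only two kinds of AESI that Protocol 9.4.2.1 names. A reader of the AESI tables would take them as complete for the liver. If the only record of an event is a diagnosis term, they are not. The gap also looks unplanned: the SAP gives no reason for limiting the hepatic group to laboratory and function-type terms when the muscle and renal groups are not limited in that way.

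**Working it through.** **1. What is on the hepatic list (SAP Appendix 5).**
- ALT, AST, blood bilirubin, hepatic enzyme, liver function test and transaminases, each as abnormal and as increased: 6 × 2 = 12 terms.
- Hypertransaminasaemia: 1 term.
- The general function term: 1 term.
- Total: 12 + 1 + 1 = 14. Terms naming hepatitis, liver injury, jaundice, hepatic failure, necrosis, cirrhosis or cholestasis: 0 of 14.

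**2. How the other groups are built (SAP Appendix 5).** There are nine other groups. Six place clinical conditions beside laboratory terms:

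| Group | Laboratory terms, for example | Clinical terms, for example |
|---|---|---|
| Muscle | creatine phosphokinase | rhabdomyolysis, myositis |
| Renal | creatinine, urea | acute kidney injury, renal failure |
| Diabetes | blood glucose | diabetes mellitus |
| Hypoglycemia | blood glucose decreased | hypoglycaemic coma |
| Uric acid | blood uric acid increased | gout |
| Hemoglobin | haemoglobin decreased | anaemia |

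The tendon and cognitive groups consist of clinical terms, and metabolic acidosis is a single term. The hepatic group is the only one with several terms that stops at laboratory and function-type findings.

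**3. When an event is lost from the AESI tables.** All three conditions must hold:
- the event is coded to a diagnosis term outside the list;
- no listed laboratory term is also recorded for that subject;
- the reported wording does not code to the general function term.

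The second condition can fail. Under Protocol 8.8.1, if a laboratory value is clinically significant, leads to discontinuation or meets a seriousness criterion, "this is considered an AE". Protocol 8.8.6 also requires an adverse event entry when AST or ALT is at least 3 × ULN with total bilirubin at least 2 × ULN, but it prescribes no term, so it does not settle which term is coded.

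**4. Size.**
- Planned treated subjects (Protocol 9.1): 100 completers + about 20 withdrawals = 120, as stated.
- Effect of one such subject on a hepatic-group proportion: 1/120 = 0.0083, or 0.83 percentage points.
- Arithmetic example, not a forecast: if 6 subjects had hepatic events and 1 was coded only to a diagnosis, the listed terms would show 5/120 = 4.2% instead of 6/120 = 5.0%.

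**5. How likely at least one such subject is.** The documents give no rate for diagnosed liver injury, so the rates p below are assumptions. Chance of at least one among 120 = 1 − (1 − p)^120.

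| Assumed p | Chance of at least one |
|---|---|
| 0.2% | 21% |
| 0.5% | 45% |
| 1% | 70% |
| 2% | 91% |

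**The case against.** The strongest reply is that little is lost and that the list suits the protocol's own usage.

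- **Other outputs hold the event.** It stays in the TEAE tables and, where it qualifies, in the serious and discontinuation tables (SAP 9.2) and the listings CT-9.1 to CT-9.3. AST, ALT and bilirubin criteria are counted from laboratory values, unscheduled visits included (SAP 9.3, Appendix 2). Hy's law cases are counted and listed (CT-10.5, CT-10.6) whatever the adverse event coding. This stands. A reader might infer that diagnosed liver injury would vanish from the safety report; the documents do not support that.
- **The eGFR breakdown is not lost.** SAP 9.2.2 runs the same eGFR categories on all TEAEs and on related TEAEs (CT-8.17-7, CT-8.18-7). This stands. The event is missing only from the AESI versions, CT-8.19 and CT-8.20.
- **No hepatic total is planned.** SAP 9.2.1 specifies SOC and PT only. This stands: the 0.83 points apply to a group proportion that the SAP does not yet produce.
- **The protocol uses hepatic impairment for enzyme changes.** Protocol 2 gives transaminase elevations as an example, and 8.7.1 follows AST, ALT and bilirubin to detect such events. This is fair in part. It explains why the laboratory terms are there, but not why diagnoses are left out, since a diagnosed liver injury also falls within Protocol 9.4.2.1.
- **Severity.** A reader might infer that the more serious an event, the less likely it is to be counted, or that the missed case would be the worst one. Nothing in the documents shows this. Serious cases have the most other routes into the report, and phase 2 had no severe events and no hepatic SAE (Protocol 2.1).
- **Phase 2 as a yardstick.** It is tempting to project the phase 2 figure, 7/141 = 4.96% (stated as 5.0%), onto 120 subjects. That is one listed term, pooled over three doses, in a trial with a Week 12 primary endpoint. It gives no rate for diagnosed injury over 52 weeks at 180 mg.

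These points limit the consequence. They do not make the AESI tables complete.

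**Conclusion.** The point holds as a gap in a term list. Followed as written, the plan leaves out of CT-8.12, CT-8.13, CT-8.19 and CT-8.20 any hepatic event coded only to an unlisted diagnosis. Each such subject is worth 0.83 percentage points of a hepatic-group proportion, assuming 120 treated subjects. The number of such subjects cannot be estimated from the documents, and the probabilities in the working rest entirely on assumed rates.

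The trial is single-arm and descriptive, and no test or stopping rule depends on these tables. The gap affects the completeness of the AESI presentation, not whether the event reaches the report. It is still worth closing, because safety is the primary objective, the liver is a named interest, and the repair is cheap.

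**What to change.** Before final lock:

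1. Add a fixed, fully enumerated set of clinical liver-injury preferred terms to the hepatic group in Appendix 5, for example hepatitis, jaundice, drug-induced liver injury, liver injury and hepatic failure. Check each against MedDRA 26.1, the version named in SAP 9.2. An open-ended instruction to include similar terms would not be enough.
2. Add an explicit hepatic-group subject incidence to CT-8.12 and CT-8.13, counting each subject once, shown with the present 14 terms and with the extended list.
3. Let CT-8.19 and CT-8.20 use the extended list.

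The cost is a revised appendix, slightly more programming and two hepatic counts to report. No new data or visits are needed. The count on the present list is kept so that the effect of the added terms is visible; the documents do not say that any earlier trial used this list, so comparability with earlier trials is not the reason.

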b)		Statins + nonstatins	
 
Fibrates, selective PPAR<math>\alpha</math> modulators: From at least 6 weeks before
 
PCSK9 inhibitors: From at least 3 months before
 
Statins and drugs other than those above: From at least 4 weeks before
 
	
 
Statins: Same dose and regimen at (or below) the lowest approved dose
 
Nonstatins: Same dose and regimen
 

c)		Only nonstatins	
 
Fibrates, selective PPAR<math>\alpha</math> modulators: From at least 6 weeks before
 
PCSK9 inhibitors: From at least 3 months before
 
Drugs other than the above: From at least 4 weeks before
 
	Same dose and regimen

- 4) Patients with a history or current condition meeting any of the following criteria 1) to 3)

Category	History or current condition	LDL-C during the screening period
1)	History of coronary artery disease	$\geq 100$ mg/dL
	Heterozygous familial hypercholesterolemia (HeFH)	
2)	Peripheral arterial disease	$\geq 120$ mg/dL
	History of non-cardiogenic cerebral infarction	
	Chronic kidney disease (Provided that it does not fall under exclusion criterion 12))	
	Type 2 diabetes mellitus (Diagnosed at least 3 months before Week -2, without falling under exclusion criterion 7))	
3)	The total score in the coronary artery disease risk prediction model using the Suita score specified by the Japan Atherosclerosis Society is $\geq 56$ points (high risk)	$\geq 120$ mg/dL
	The total score in the coronary artery disease risk prediction model using the Suita score specified by the Japan Atherosclerosis Society is $\geq 41$ and $\leq 55$ points (intermediate risk)	$\geq 140$ mg/dL

- 5) Patients with fasting TG levels of <400 mg/dL at Week –2
- Rollover subjects from the phase 3 confirmatory trial
  - 1) Patients who provide written informed consent prior to the start of the trial
  - 2) Subjects who have completed the 12-week treatment period in the phase 3 confirmatory trial (Protocol No. 346-102-00002) and do not meet the discontinuation criteria for the IMP at Week 12

[Rationale for the inclusion criteria]

- Newly Enrolled Subjects
  - 1) This criterion is set based on ethical considerations.
  - 2) The lower limit of age is set as adults with sufficient ability to provide informed consent. The upper limit of age is set at 85 years in consideration of safety.

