9.2.2 Subgroup Analyses of Adverse Events

The number of subjects with TEAEs and the incidence will be calculated by SOC and PT for each of the following subgroups. Treatment-emergent AEs that are potentially causally related to the IMP will be summarized in the same manner. Statin intensity categories and types are shown in [Appendix 6](#). In the data for each statin type, subjects who use multiple medications will be excluded from the summarization.

- Sex (Male, Female)
- Familial hypercholesterolemia (Yes, No)
- Diabetes mellitus (Yes, No)
- Age (<65 years, ≥65 years and <75 years, ≥75 years)
- Statin use (Yes, No)
- BMI (<25 kg/m², ≥25 kg/m² and <30 kg/m², ≥30 kg/m²)
- eGFR (<60 mL/min/1.73 m², ≥60 mL/min/1.73 m² and <90 mL/min/1.73 m², ≥90 mL/min/1.73 m²)
- Statin intensity (Low-intensity statins, High-intensity statins, No statins)
- Statin type (atorvastatin calcium trihydrate, fluvastatin sodium, pitavastatin calcium, pravastatin sodium, rosuvastatin calcium, simvastatin, no statins)

For AEs of special interest, the number of subjects with the events and the incidence will be calculated by SOC and PT for each of the following subgroups. Adverse events of special interest that are potentially causally related to the IMP will be summarized in the same manner.

- eGFR (<60 mL/min/1.73 m², ≥60 mL/min/1.73 m² and <90 mL/min/1.73 m², ≥90 mL/min/1.73 m²)

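### The SAP's renal AESI group has no chronic kidney disease term, so any event coded to one would be left out of the AESI tables, including those by eGFR

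*SAP*

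**What the plan says.** SAP 9.2.1 tabulates AESIs by system organ class and preferred term, and refers to Appendix 5 for their classification. Appendix 5 is a fixed list of coded terms. Its "Renal dysfunction-related" group has 15:

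- five clinical terms: "Acute kidney injury", prerenal failure, renal failure, "Renal impairment" and oliguria;
- ten laboratory or function terms, such as "Glomerular filtration rate decreased" and the creatinine, clearance and urea terms.

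Protocol 5.2.1, criterion 4, admits newly enrolled subjects on the basis of a category 2 condition. One is "Chronic kidney disease (Provided that it does not fall under exclusion criterion 12". Exclusion criterion 12 removes only those who have renal disease together with eGFR of 30 or less.

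The diabetes group in Appendix 5 contains "Type 2 diabetes mellitus", which is also a category 2 entry condition.

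SAP 9.2.2 states: "For AEs of special interest, the number of subjects with the events and the incidence will be calculated by SOC and PT", and eGFR (below 60, 60 to below 90, 90 or above) is the only subgroup given for AESIs. The resulting tables are CT-8.19 and, for IMP-related events, CT-8.20.

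On reporting, Protocol 8.8.2 says that "if worsening of the condition is observed on Day 1 or later, the AE should be reported as a new AE in the eCRF". Earlier in the same paragraph it limits the reporting of disease progression to unusual, severe or unexpected features.

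**The concern.** Membership of the AESI tables is decided by the Appendix 5 list alone. A renal diagnosis missing from the list is missing from those tables, however relevant it is. Chronic kidney disease is the one renal diagnosis that the protocol itself names as a reason for entry, so some subjects will carry it at baseline and others could receive it as a new diagnosis during 52 weeks.

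The only AESI subgroup analysis is by renal function. If events in subjects with reduced eGFR were coded to an unlisted term, the table meant to show AESIs by renal function could understate them. Renal findings also matter to the sponsor: Protocol 8.7.1 names creatinine and urea nitrogen increases for careful monitoring.

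**Working it through.** **1. The plan's own figure.** Protocol 9.1 and SAP section 4 give 100 completers plus about 20 withdrawals: 100 + 20 = 120. Equivalently, 100 / (1 − 20/120) = 120. The figure reproduces and is the denominator used below.

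**2. Count of the list.** There are 15 terms in the renal group. The only one containing the word kidney is "Acute kidney injury". Chronic kidney disease terms: 0 of 15.

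**3. Comparison of two entry conditions.** Type 2 diabetes is a category 2 entry condition and is on its AESI list. Chronic kidney disease is a category 2 entry condition and is not on its list. The SAP therefore does not leave out entry diagnoses on principle, and it gives no reason for the difference.

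**4. Can such an event be reported?**

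- A first diagnosis after the start of treatment is a treatment-emergent event under Protocol 8.8.1, with no need for the worsening rule.
- Protocol 8.8.1 also counts an event continuous from baseline that worsens after the start of treatment.
- Protocol 8.8.2 prefers one unifying diagnosis over separate signs, which favours a diagnosis over a laboratory term.
- Protocol 8.8.2 also restricts progression events to unusual, severe or unexpected features. Expected progression may therefore not be reported at all.

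So such events are possible, but not every worsening becomes one.

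**5. Which tables are affected?** An event coded to an unlisted term is absent from CT-8.12, CT-8.13, CT-8.19 and CT-8.20. It remains in CT-8.2 (all treatment-emergent events) and CT-8.17-7 (the same events by eGFR).

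**6. Size per subject.** The documents do not give the number with eGFR below 60. Assume 15% to 40% of 120. One subject whose only AESI is so coded changes the stratum incidence by 100/n points.

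| Assumed share | n in stratum | Change in stratum | Change overall |
|---|---|---|---|
| 15% | 0.15 × 120 = 18 | 100/18 = 5.6 points | 100/120 = 0.83 points |
| 40% | 0.40 × 120 = 48 | 100/48 = 2.1 points | 100/120 = 0.83 points |

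**7. Size for an assumed event rate.** Suppose that 5% of the stratum has a reported worsening and no other AESI. The shortfall is 5% times the fraction coded to the unlisted term: 5 × 0 = 0 points if none, 5 × 0.5 = 2.5 points if half, 5 × 1 = 5.0 points if all. Neither the rate nor the fraction is in the documents, so the lower end of the range is zero.

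**The case against.** The strongest reply is that nothing may be missed. Worsening renal function can be coded to "Renal impairment", renal failure, "Glomerular filtration rate decreased" or a creatinine term, all of which are listed. Chemistry is taken at every scheduled visit, so laboratory terms are a likely route. Protocol 8.8.2 may keep expected progression out of the AE data altogether. Its sentence on worsening from Day 1 follows one about an AE already reported, so its reach to a condition in the medical history is unclear. All of this stands, and it is why the size may be zero.

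It is also true that no event is lost. CT-8.17-7 and CT-8.18-7 show all and IMP-related treatment-emergent events for the same eGFR strata, and creatinine and urea nitrogen have descriptive, shift and threshold analyses under SAP 9.3. The protocol requires no renal AESI group, so the omission breaks no protocol rule. The SAP specifies no count per Appendix 5 group: adding a term adds a preferred-term row and may change a system organ class subtotal.

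These points limit the consequence, but they do not explain why the SAP's own renal group omits this diagnosis while its diabetes group includes the corresponding one.

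A reader might go further and infer that renal AESIs are certainly undercounted, almost all in the stratum below 60, and that CT-8.19 would wrongly show no added renal risk there. The documents do not support that. They do not say how events will be coded, the chronic kidney disease criterion gives no eGFR cut-off, and 15 renal terms remain in the table.

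**Conclusion.** The omission is real, and correcting it is a cheap improvement. A treatment-emergent event coded to a chronic kidney disease term would be left out of all four AESI table sets, and the AESI-by-eGFR tables could understate renal events as a result.

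The total effect cannot be estimated from the documents. The figure of 5.6 to 2.1 points is per affected subject. It rests on the assumed 15% to 40% share below 60 and on that subject having no other AESI. Concentration in that stratum is plausible but not shown. That chronic kidney disease has its own preferred term in MedDRA 26.1 is also an assumption, which the sponsor can check directly.

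**What to change.** Before the final analysis:

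1. Look up in MedDRA 26.1, the version named in SAP 9.2, the preferred term or terms to which chronic kidney disease codes, and add them to the renal group in Appendix 5.
2. Produce CT-8.12, CT-8.13, CT-8.19 and CT-8.20 on the revised list.
3. Reconcile the two statements in Protocol 8.8.2, the limit on reporting progression and the rule on worsening from Day 1, so that sites know which governs worsening of a pre-existing entry condition.

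The cost is one or two appendix rows and a clarifying sentence. Renal AESI counts may rise slightly. No new data collection is needed.
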